#### **9.8. Dilated Fundus Examination**

A dilated fundus examination is performed at Baseline and the Month 12, 24, 36, and 48 visits. Assessments of optic nerve head, macula, peripheral retina, iris, and vitreous will be provided for each eye individually.

Findings at each visit will be summarized by stage, visit and treatment group using descriptive statistics.

Dilated fundus examination results will be provided in subject data listings.

#### **9.9. Intraocular Pressure**

Intraocular pressure (mmHg) is measured at Baseline and the Month 6, 12, 18, 24, 30, 36, 42, and 48 visits. Measurement of intraocular pressure will be provided for each eye individually.

Observed values at each visit and changes from Baseline to each post-baseline visit will be summarized by stage, visit and treatment group using descriptive statistics. For Stage 2, the Stage 2 baseline (Month 36) will be used for the change from baseline calculation.

Intraocular pressure measurements will be provided in subject data listings.

This document is confidential.

## 10. Quality of Life

### 10.1. Modified Amblyopia Treatment Index (mATI)

The Amblyopia Treatment Index (ATI) was developed by the Pediatric Eye Disease Investigator Group to measure the impact or burden of amblyopia treatment on the child and the family. The Modified Amblyopia Treatment Index (mATI) consists of 2 questionnaires. One is completed by a Parent/ Guardian while the second is completed by the subject at the Month 42 and Month 48 visits. The questionnaires consist of 16 or 15 questions respectively using a five-point Likert scale for each question.

The questionnaires will be scored to an Overall Score and 3 subscales (Adverse Event, Treatment Compliance, and Social Stigma). Questionnaires with 3 or more missing or not applicable responses will not be scored or analyzed. For questionnaires with 1 or 2 missing or not applicable responses, these responses will be imputed with the average score for all completed items. See Table 4: Modified Amblyopia Treatment Index Scoring for scoring methodology.

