**Table 4: Modified Amblyopia Treatment Index Scoring**

Score	Parent	Child
Overall	Mean of (Items 1*, 2, 3, 4, 5, 6, 7, 8, 9*, 10, 11, 12, 13, 14*, 15, 16)	Mean of (Items 1, 2, 3, 4, 5, 6, 7, 8*, 9, 10, 11, 12, 13*, 14, 15)
Adverse effect subscale	Mean of (Items 2, 3, 4, 7, 8, 9*, 13, 15)	Mean of (Items 2, 3, 4, 8, 9, 12, 14)
Treatment compliance subscale	Mean of (Items 1*, 5, 6, 10, 12)	Mean of (Items 1, 5, 9, 11)
Social stigma subscale	Item 11	Item 10

\*Reverse scoring applied. Value used in scoring = (6- reported score)

Overall and subscale scores for mATI will be summarized by visit and Stage 2 treatment group using descriptive statistics as both a continuous and categorical variable. Individual item and all scores will be listed.

This document is confidential.

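### When the single social stigma item of the mATI is unanswered or not applicable, the SAP's imputation rule reports a stigma score that contains no stigma answer

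*SAP*

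**What the plan says.** SAP section 10.1 describes two questionnaires, one for the parent or guardian and one for the child, completed at Months 42 and 48: "The questionnaires consist of 16 or 15 questions respectively using a five-point Likert scale for each question". On scoring it says: "The questionnaires will be scored to an Overall Score and 3 subscales (Adverse Event, Treatment Compliance, and Social Stigma" (the closing bracket follows in the text).

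The missing-data rule has two parts. The first is a cut-off: "Questionnaires with 3 or more missing or not applicable responses will not be scored or analyzed". The second covers everything below it: "For questionnaires with 1 or 2 missing or not applicable responses", "these responses will be imputed with the average score for all completed items". Both parts count a not-applicable response as missing. Neither part depends on which item is affected or which subscale it belongs to.

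Table 4 maps items to scores. Its stigma row reads "Social stigma subscale Item 11 Item 10", that is, one item on each form. A footnote to the same table covers the starred items: "Value used in scoring = (6- reported score" (closing bracket omitted). Neither section 10.1 nor Table 4 says whether the average used for imputation is taken before or after that reversal.

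The Overall and subscale scores are then summarised by visit and Stage 2 treatment group, both as continuous and as categorical variables (Table 14.3.4.3.1 in the SAP's Index of Tables).

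**The concern.** Filling a gap with the mean of the remaining items can be defended when those items measure the same thing. A one-item subscale has no remaining items. If its only item is blank, the rule borrows entirely from answers about adverse effects, about compliance, and from items that Table 4 places in no subscale. The result is printed under the stigma label and counted in the stigma n.

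The same happens when the respondent says the question does not apply. That response carries information, but the rule turns it into a numerical stigma score.

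What is at stake is whether the stigma line of the quality-of-life table means what it says. Differences between arms in side-effect answers could also reach that line without any stigma answer behind them.

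**Working it through.** The SAP states no figure to reproduce here, so the check applies the section 10.1 rule to the Table 4 item map.

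**Inputs from the documents**
- Parent form: 16 items. Adverse effect has 8 (2, 3, 4, 7, 8, 9, 13, 15), compliance has 5 (1, 5, 6, 10, 12), stigma has 1 (11). Items 14 and 16 are in no subscale. Items 1, 9 and 14 are reverse-scored.
- Child form: 15 items. Adverse effect has 7 (2, 3, 4, 8, 9, 12, 14), compliance has 4 (1, 5, 9, 11), stigma has 1 (10). Item 9 is in both multi-item subscales. Items 6, 7, 13 and 15 are in no subscale. The Overall row stars items 8 and 13 for reversal.
- The stigma item is in no other subscale on either form and is not reversed.

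**Step 1: content of the filled stigma score**
- Parent, Item 11 blank: mean of 8 + 5 + 2 = 15 items, or 14 if a second item is blank.
- Child, Item 10 blank: mean of (7 + 4 − 1) + 4 = 14 items, or 13 if a second item is blank.
- Stigma answers contributing: 0 on both forms.

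**Step 2: relation to the Overall score.** Let m be the mean of the completed items after reversal. On the parent form, Overall = (15m + m)/16 = m, and with a second item also blank, (14m + 2m)/16 = m. The filled stigma score therefore equals the Overall score exactly. It also follows that leaving stigma missing does not change Overall, provided reverse-scored values are averaged.

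**Step 3: one respondent (assumed answers, after reversal).** Adverse effect items all 4, every other item 2.
- Parent: (8 × 4 + 7 × 2)/15 = 46/15 = 3.07.
- Child: (7 × 4 + 7 × 2)/14 = 42/14 = 3.00.

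These values result whatever the respondent's stigma level is.

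**Step 4: group mean.** Let f be the share with the stigma item unanswered, S the mean of answered stigma items, and M the mean of the other items. Then shift = f × (M − S). The documents give none of the three, so all values are assumptions.

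| S | M | f | Shift in stigma mean |
|---|---|---|---|
| 1.3 | 2.4 | 10% | 0.10 × 1.1 = 0.11 |
| 1.3 | 2.4 | 20% | 0.20 × 1.1 = 0.22 |
| 1 | 3 | 5% | 0.05 × 2 = 0.10 |
| 1 | 3 | 30% | 0.30 × 2 = 0.60 |

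**Step 5: leakage between arms.** If adverse effect answers on the parent form are one point higher in one arm, the filled score in that arm rises by 8/15 = 0.53. With f at 10 to 20% in both arms, that adds 0.05 to 0.11 to the difference in stigma means.

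**Step 6: order of reversal and imputation.** Take a parent whose scored burden is 2 on every item, so the raw answer on a reversed item is 6 − 2 = 4, with one reversed item blank.
- Reverse first, then average: 2.00, the correct value.
- Average raw answers and insert unchanged: (13 × 2 + 2 × 4)/15 = 34/15 = 2.27.
- Average raw answers, then flip: 6 − 2.27 = 3.73.

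The last reading is 1.73 too high on that item. In the reported scores this is 1.73/16 = 0.11 on Overall and, depending on the item, 1.73/8 = 0.22 on adverse effect (Item 9) or 1.73/5 = 0.35 on compliance (Item 1).

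**The case against.** The best case for leaving the rule alone is that little depends on it. The protocol synopsis makes the questionnaire voluntary. It is collected only at Months 42 and 48, is summarised descriptively, and is not among the primary, secondary, tertiary or exploratory endpoints in SAP section 4. Blanks may be rare: a footnote to the protocol's Schedule of Procedures has site staff read out the questions and response choices and enter the answers, and the visit descriptions have them verify completion. Individual item responses are listed (Listing 16.2.8.2.6), so the actual stigma answers can be recovered. All of this stands and limits the importance of the point. It does not repair the rule. Staff help may reduce blanks but does not prevent a not-applicable response, and a listing does not correct the summary table.

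It could also be said that the same rule applies in every arm. That helps only if the arms have similar rates of unanswered stigma items and similar answers on the other items, as step 5 shows.

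One might hope that the average is meant within each subscale. The wording does not allow it: the rule is set for the questionnaire as a whole and names all completed items.

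Three stronger readings are tempting, and the documents do not support them.
- A reader might infer that the SAP flips imputed reversed items the wrong way. It gives no order, and an imputed value is arguably not a reported score at all. The 3.73 above is one of three possible results.
- A reader might infer that not applicable is the natural reply for drops given at home at bedtime, and so a frequent one. The wording of the stigma items and the response rates are not in the documents.
- A reader might object equally to filling adverse effect items from compliance items and the reverse. Those subscales normally keep answers of their own, so the choice there is one of convention. Whether it follows the instrument's own scoring guidance cannot be checked: the SAP's only listed reference is an optics text.

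**Conclusion.** The point holds for the single-item subscale. Followed as written, section 10.1 and Table 4 together produce a stigma score with no stigma answer in it whenever that item is one of one or two unanswered or not-applicable responses. This follows from the text and needs no assumption.

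Its size in the trial is unknown. The shifts of 0.11 to 0.22, and 0.10 to 0.60 under the harsher inputs, rest entirely on assumed rates and means. If no stigma item is left blank or marked not applicable, the effect is zero.

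The order of reversal and imputation is an ambiguity to close, not a demonstrated error. Overall this is a minor correction to a descriptive Stage 2 summary, with no bearing on the efficacy conclusions.

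**What to change.** In section 10.1:
- State that the social stigma score is left missing when parent Item 11 or child Item 10 is missing or not applicable. The item should still count towards the cut-off of three.
- Report the number of not-applicable stigma responses by visit and Stage 2 treatment group, separately from missing responses.
- State that starred items are reverse-scored before any average is taken, and that imputed values are not reversed again.

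The cost is a few sentences in the SAP, a small change to the scoring code, and a slightly smaller n on the stigma line. With averaging done on reverse-scored values, the Overall score is the same as before. Every reported stigma score is then a whole number from 1 to 5, which also removes a practical difficulty: an imputed stigma score is usually fractional, and the SAP gives no rule for placing it in a category for the planned categorical summary.

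Restricting imputation to items of the same subscale elsewhere in the questionnaire is an option, but this point does not require it.

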**Table 4: Modified Amblyopia Treatment Index Scoring**

Score	Parent	Child
Overall	Mean of (Items 1*, 2, 3, 4, 5, 6, 7, 8, 9*, 10, 11, 12, 13, 14*, 15, 16)	Mean of (Items 1, 2, 3, 4, 5, 6, 7, 8*, 9, 10, 11, 12, 13*, 14, 15)
Adverse effect subscale	Mean of (Items 2, 3, 4, 7, 8, 9*, 13, 15)	Mean of (Items 2, 3, 4, 8, 9, 12, 14)
Treatment compliance subscale	Mean of (Items 1*, 5, 6, 10, 12)	Mean of (Items 1, 5, 9, 11)
Social stigma subscale	Item 11	Item 10

\*Reverse scoring applied. Value used in scoring = (6- reported score)

Overall and subscale scores for mATI will be summarized by visit and Stage 2 treatment group using descriptive statistics as both a continuous and categorical variable. Individual item and all scores will be listed.

This document is confidential.

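### In the child mATI key, the adverse-effect row contradicts the overall score on the direction of item 8 and shares item 9 with the compliance row

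*SAP*

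**What the plan says.** SAP section 10.1 introduces a parent and a child form: "The questionnaires consist of 16 or 15 questions respectively using a five-point Likert scale for each question". Table 4 gives the scoring key, with an asterisk explained as "Reverse scoring applied. Value used in scoring = (6- reported score".

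Child key:
- Overall: the mean of all 15 items, with items 8 and 13 asterisked.
- Adverse effect: "Mean of (Items 2, 3, 4, 8, 9, 12, 14", with no asterisk.
- Treatment compliance: "Mean of (Items 1, 5, 9, 11".
- Social stigma: item 10.

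Parent key:
- Overall: "Mean of (Items 1*, 2, 3, 4, 5, 6, 7, 8, 9*, 10, 11, 12, 13, 14*, 15", and item 16.
- Adverse effect: "Mean of (Items 2, 3, 4, 7, 8, 9*, 13, 15".
- Treatment compliance: "Mean of (Items 1*, 5, 6, 10, 12".
- Social stigma: item 11.

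On use, the SAP says: "Overall and subscale scores for mATI will be summarized by visit and Stage 2 treatment group using descriptive statistics", treating the scores both as continuous and as categorical. The protocol synopsis makes participation voluntary and places the questionnaires at Months 42 and 48.

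**The concern.** Two entries in the child adverse-effect row conflict with their surroundings. Item 8 is reversed in the overall score but enters this subscale as reported. Item 9 contributes to two subscales, which no item does on the parent form.

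Programmers will code the key as printed. If item 8 needs reversing, leaving it as reported pulls the adverse-effect mean against the other six items. If item 9 belongs to only one subscale, the other carries an item that is not its own. The score at stake is the children's own report of adverse effects, tabulated by Stage 2 treatment group in SAP Table 14.3.4.3.1.

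**Working it through.** All inputs come from SAP section 10.1 and Table 4. The SAP states no figure to reproduce, so the check compares item membership and asterisks across rows and then sizes the effect.

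**Step 1: direction.** Parent items 1, 9 and 14 are reversed in the overall score. Items 1 and 9 also enter a subscale, and both keep their asterisk there. Child items 8 and 13 are reversed in the overall score. Only item 8 enters a subscale, and it loses its asterisk there.

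**Step 2: overlap.** No parent item is in two subscales. On the child form, the adverse-effect and compliance rows share item 9.

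**Step 3: parent-to-child numbering.** The parent form has one more item than the child form. Suppose parent item 6 is dropped and every later item moves down by one:

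| Row | Parent | Implied child list | Printed child list |
|---|---|---|---|
| Compliance (membership) | 1, 5, 6, 10, 12 | 1, 5, 9, 11 | 1, 5, 9, 11 |
| Stigma | 11 | 10 | 10 |
| Reversed in overall | 1, 9, 14 | 1, 8, 13 | 8, 13 |
| In no subscale | 14, 16 | 13, 15 | 6, 7, 13, 15 |
| Adverse effect | 2, 3, 4, 7, 8, 9*, 13, 15 | 2, 3, 4, 6, 7, 8*, 12, 14 | 2, 3, 4, 8, 9, 12, 14 |

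Membership fits in the compliance and stigma rows and breaks in the adverse-effect row. The extra unassigned items, 6 and 7, are the two that the mapping would place in that row. The one other departure is item 1, which is reversed on the parent form and nowhere on the child form.

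**Step 4: size.** Five response points and a 6-minus rule imply coding from 1 to 5.

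- Reversing item 8 (raw response x) in the 7-item mean changes it by ((6 - x) - x)/7 = (6 - 2x)/7. For x = 1, 2, 3, 4, 5 this is +0.571, +0.286, 0, -0.286, -0.571.
- Take higher scores as more burden and the overall row's direction for item 8 as correct. A child with maximal burden on every item then scores (6 × 5 + 1)/7 = 4.43 as printed and 5.00 with reversal. With minimal burden the scores are (6 × 1 + 5)/7 = 1.57 and 1.00.
- If instead the overall row is the wrong one, the 15-item mean changes by (6 - 2x)/15, at most 4/15 = 0.27.
- Removing item 9 from the adverse-effect row changes it by (m - x)/7, where m is the mean of the other six scored items: at most 4/7 = 0.57. Removing it from compliance instead gives (m - x)/4, with m now the mean of the other three: at most 4/4 = 1.00.
- For two treatment groups whose raw item 8 means differ by d, reversal changes the difference in adverse-effect means by -2d/7. The documents give no response data from which to put a value on d.

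**The case against.** The strongest reply is that the questionnaires and their scoring source are not in the documents.

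- **Overlap.** Nothing in the SAP requires the subscales to be disjoint, and the forms differ in length, so a shared item 9 could be deliberate. This stands: the overlap is unexplained and has no parent counterpart, but it is not proven wrong.
- **Unassigned items.** The parent key also leaves two items outside every subscale. This stands too: the absence of items 6 and 7 is not a fault in itself.
- **The mapping.** It does not reproduce the reversal of item 1, and it implies eight adverse-effect items where seven are printed. A reader might take 2, 3, 4, 6, 7, 8*, 12, 14 as the right list. The documents support it only as a plausible reconstruction.
- **The asterisk.** One could have been lost when the PDF was read. All seven others in the table survived, and a lost asterisk would not explain the second item 9.
- **The sizes.** The 0.57 figures are extremes for one child and hold for the printed 7-item list. If item 9 is dropped, reversing item 8 moves a 6-item mean by up to 4/6 = 0.67. At a mid-scale answer to item 8 the reversal effect is zero.
- **Importance.** The mATI is in none of the endpoint lists in SAP sections 4.1 to 4.4, it is not tested, and item responses will be listed, so scores could be recomputed. This limits the consequence but is no reason to program a contradictory key.

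None of these replies explains how item 8 could run in one direction in the overall score and in the other in the subscale.

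**Conclusion.** The concern holds for the child adverse-effect row. The contradiction on item 8 is definite, taking the table as it reads: at least one of the child overall and adverse-effect scores is miscoded. The parent key's practice and the numbering pattern point to the subscale row, but that is inference. The repeated item 9 is a query of the same origin. For one child, each entry can move the printed 7-item mean by up to 0.57, assuming 1-5 coding.

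A reader might infer that the child subscale scores in general will be wrong. The documents do not support that. Social stigma, which is item 10 alone, is untouched, and compliance is affected only if item 9 does not belong there. No primary or secondary efficacy result is touched.

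**What to change.** Before Stage 2 scores are programmed, check the child column of Table 4 against the questionnaire's scoring source and amend the adverse-effect row:

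- give item 8 one direction wherever it is used;
- keep item 9 only in the subscale or subscales that the instrument specifies, and say so if it belongs to both;
- confirm whether items 6 and 7 belong in the adverse-effect row;
- confirm that child item 1 is not reversed, unlike parent item 1.

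The cost is one table row, the matching lines of the scoring program and a look at the instrument. SAP section 11 provides no Stage 2 results at the Stage 1 analysis, so that analysis does not depend on the correction.

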## 11. Interim Analyses

In order to determine the efficacy of Atropine Sulfate Ophthalmic Solution in progression of childhood myopia, an analysis will be performed after all subjects complete or withdraw from Stage 1. At that time, on Stage 1 treatment assignments will be unblinded and no analyses or summaries will be provided for Stage 2 results. All study personnel, not including Investigators, site staff, and clinical research associates (CRAs), may be unblinded for Stage 1 at this time.

All analyses will be performed as documented in the SAP. No decisions regarding the study or changes in the study are to be made at that time.

This document is confidential.

## 13. Programming Considerations

All tables, figures, listings (TFLs), and statistical analyses will be generated using SAS for Windows, Release 9.4 (SAS Institute Inc., Cary, NC, USA). Computer-generated table, listing and figure output will adhere to the following specifications.

### 13.1. General Considerations.

- One SAS program can create several outputs, or a separate SAS program will be created for each output.
- Each output will be stored in a separate file.
- Output files will be delivered in Word format or portable document format pdf.
- Numbering of TFLs will follow ICH E3 guidance

### 13.2. Table, Listing, and Figure Format

#### 13.2.1. General

- All TFLs will be produced in landscape format on American letter size, unless otherwise specified.
- All TFLs will be produced using the Courier New font, size 8 which is the smallest acceptable point size for the Regulatory Authorities.
- The data displays for all TFLs will have a minimum blank 1-inch margin on all 4 sides.
- Headers and footers for figures will be in Courier New font, size 8 which is the smallest acceptable point size for the Regulatory Authorities.
- Legends will be used for all figures with more than 1 variable, group, or item displayed.
- TFLs will be in black and white (no color), unless otherwise specified
- Specialized text styles, such as bolding, italics, borders, shading, and superscripted and subscripted text, will not be used in the TFLs, unless otherwise specified. On some occasions, superscripts 1, 2, or 3 may be used (see below).
- Only standard keyboard characters will be used in the TFLs. Special characters, such as non-printable control characters, printer-specific, or font-specific characters, will not be used. Hexadecimal-derived characters will be used, where possible, if they are appropriate to help display math symbols (e.g.,  $\mu$ ). Certain subscripts and superscripts (e.g.,  $\text{cm}^2$ , Cmax) will be employed on a case-by-case basis.
- Mixed case will be used for all titles, footnotes, column headers, and programmer-supplied formats, as appropriate.

#### 13.2.2. Headers

- All output should have the following header at the top left of each page:
- Vyluma, Inc. Protocol CP-NVK002-0001 (Syneos Health study number 1)

This document is confidential.

- Draft/Final Run <date>
- All output should have Page n of N at the top or bottom right corner of each page. TFLs are internally paginated in relation to the total length (i.e., the page number should appear sequentially as page n of N, where N is the total number of pages in the table).
- The date output was generated should appear along with the program name as a footer on each page.

#### 13.2.3. Display Titles

- Each TFL are identified by the designation and a numeral. (i.e., Table 14.1.1). ICH E3 numbering is strongly recommended, but sponsor preferences are obtained before final determination. A decimal system (x.y and x.y.z) are used to identify TFLs with related contents. The title is centered. The analysis set are identified on the line immediately following the title. The title and table designation are single-spaced. A solid line spanning the margins will separate the display titles from the

Table x.y.z  
First Line of Title  
Second Line of Title if Needed  
(ITT Analysis Set)

